3.9 Discontinuation of investigational product

3.9.1 Criteria for discontinuation of investigational product due to worsening LN or SLE (at any time)

Blinded IP will be discontinued in subjects who meet pre-defined criteria for worsening LN or SLE. Subjects may receive rescue treatment as clinically indicated. Subjects who had their IP discontinued will be followed according to the study schedule. These subjects will be followed until Week 52 (or for a minimum of 12 weeks after last dose of IP for subjects for whom IP was discontinued within 12 weeks prior to Week 52). If discontinuation occurs during the second year extension period, subjects will be followed until Week 104 (or for a minimum of 12 weeks after last dose of IP for subjects for whom IP was discontinued within 12 weeks prior to Week 104).

- >30% decrease in eGFR compared to baseline due to LN and eGFR <60 mL/min/1.73 m² (on two independent samples) or
- Increase in renal or extra-renal lupus activity requiring prohibited systemic immunosuppressive treatment (eg, cyclophosphamide, rituximab, belimumab)
- Receipt of >1 methylprednisolone pulse after the day of randomisation
- Receipt of any methylprednisolone pulse after Week 8
- The IP will be discontinued if MMF is discontinued and another immunosuppressant is initiated

3.9.2 Criteria for discontinuation of investigational product for worsening of LN or SLE at Week 12 and Week 24

- eGFR <75% of baseline and <60 mL/min/1.73 m² (on two independent samples) or
- Nephrotic range UPCR (confirmed by a second measurement at least two weeks after the first measurement):
 - Subjects with 24-hour UPCR ≤3 mg/mg at baseline will be withdrawn if 24-hour UPCR increases by >50% from baseline to >3.5 mg/mg

- Subjects with 24-hour UPCR >3 mg/mg at baseline will be withdrawn if 24-hour UPCR at Week 24 >3.5 mg/mg and there is $<60\%$ improvement from baseline or
- Inability to adhere to corticosteroids requirements:
 - Inability to reduce OCS to ≤ 15 mg/day prednisone-equivalent at Week 12
 - Inability to reduce OCS to <15 mg/day by Week 24

Subjects who exceed the maximum daily OCS dose at the Week 12 or Week 24 visits may continue to receive IP if the current dose is part of a temporary increase in OCS dose (eg, protocol-allowed burst and taper). Subjects who cannot be returned to their pre-increase dose within 14 days from the start of the increase will have their IP discontinued at the next visit.

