7.7.2 Excluded medications

7.7.2.1 Medications that are excluded after signing the ICF

Receipt of any of these medications leads to immediate discontinuation of IP:

- Cyclophosphamide
- IFN therapy (α 2a and 2b, beta 1a and 1b, and pegylated IFNs α 2a and 2b)
- Investigational agents
- Biologic immunomodulators (including belimumab, abatacept, rituximab)
- Tofacitinib
- Live or attenuated vaccines (the Sponsor recommends that Investigators ensure all subjects are up to date with required vaccinations prior to entry into the study)
- BCG vaccine

- Any immunoglobulin (Ig) therapy
- Exceeding the number or dose of protocol-allowed methylprednisolone pulses (oral or IV)
- Any medications or treatment modality listed in [Appendix H](#)

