1.2.1 Standard of care immunosuppressive treatment for lupus nephritis

Standard of care treatment for LN will consist of the combination of MMF and corticosteroids. From the day of randomisation onwards until the end of subject's participation in the study including the second year extension period, MMF will be supplied by the Sponsor and Sponsor's delegate to subjects. The target dose of MMF will be 2 gm/day during the first year of the study, where the dose is titrated to the target dose between randomisation and not later than Week 8. It is not mandatory for a subject to receive 2 gm/day of MMF if local treatment standards dictate a lower dose to be given (e.g., for constitutionally small subjects). During the 52-week double-blind treatment period, the minimum dose of MMF is 1.0 gm/day between Week 8 and Week 52. Adjustments of the dose due to suboptimal response, toxicity, or intolerability are allowed if needed. A maximum dose of 3.0 gm/day is allowed up to Week 24 for subjects with suboptimal response between Weeks 8 and 24, which needs to be reduced to ≤ 2.0 gm/day by Week 32. The dose of MMF has to be stable from Week 40 to Week 52.

In the second year, extension period, MMF dose should be ≤ 2.0 gm/day or \leq Week 52 dose, whichever is lower. If MMF dose is > 2.0 gm/day at Week 52, taper to ≤ 2 gm/day will be required by Week 60. Failure to do so will lead to withdrawal from IP. A decrease in MMF dose is allowed at the investigator's discretion between Week 52 to Week 92. The dose of MMF must be stable from Week 92 to Week 104.

Subjects may enter the study taking daily OCS at a maximum dose of 0.5 mg/kg/day of prednisone-equivalent not to exceed 40 mg/day. In addition, subjects will receive IV (or oral,

if applicable) methylprednisolone pulse 500 mg on the day of randomisation, prior to receiving the IP, unless they have received a methylprednisolone pulse of ≥ 500 mg within 10 days prior to randomisation. Subjects may receive one additional (optional) dose of IV (or oral, if applicable) methylprednisolone pulse (≤ 500 mg) for renal or extra-renal disease activity after the Week 0 (Day 1) visit up to and including the Week 8 visit. Methylprednisolone pulse can be administered on two consecutive days but the cumulative dose must not exceed 500 mg.

Details on other medications permitted during the study are given in [Appendix A](#) to [Appendix C](#).

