1.2.5 Discontinuation of IP

Criteria for discontinuing IP for worsening of LN or SLE (at any time):

Blinded IP will be discontinued in subjects who meet pre-defined criteria for worsening LN or SLE. Subjects may receive rescue treatment as clinically indicated. Subjects who had their IP discontinued will be followed according to the study schedule and should have a 24-hour UPCR measurement within 4 weeks of the decision to discontinue IP and before the start of a new treatment for LN. These subjects will be followed until Week 52 (or for a minimum of 12 weeks after last dose of IP for subjects for whom IP was discontinued within 12 weeks prior to Week 52). If discontinuation occurs during the second year extension period, subjects will be followed until Week 104 (or for a minimum of 12 weeks after last dose of IP for subjects for whom IP was discontinued within 12 weeks prior to Week 104).

- >30% decrease in eGFR compared to baseline due to LN **and** eGFR <60 mL/min/1.73 m² (on two independent samples) **or**
- Increase in renal or extra renal lupus activity requiring prohibited systemic immunosuppressive treatment (e.g. cyclophosphamide, rituximab, belimumab)
- Receipt of >1 methylprednisolone pulse after the day of randomisation
- Receipt of any methylprednisolone pulse after Week 8
- The IP will be discontinued if MMF is discontinued and another immunosuppressant is initiated

Criteria for discontinuation of IP for worsening of LN or SLE at Week 12 and Week 24:

- eGFR <75% of baseline and <60 mL/min/1.73 m² (on two independent samples) **or**
- Nephrotic range UPCR (confirmed by a second measurement at least two weeks after the first measurement):

- Subjects with 24-hour UPCR ≤ 3 mg/mg at baseline will be withdrawn if 24-hour UPCR increases by $>50\%$ from baseline to >3.5 mg/mg
- Subjects with 24-hour UPCR >3 mg/mg at baseline will be withdrawn if 24-hour UPCR at Week 24 >3.5 mg/mg and there is $<60\%$ improvement from baseline **or**
- Inability to adhere to corticosteroids requirements:
 - Inability to reduce OCS to ≤ 15 mg/day prednisone-equivalent at Week 12
 - Inability to reduce OCS to <15 mg/day by Week 24

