4.1.4.3 Non-responder imputation

For the analysis of the secondary and exploratory efficacy responder endpoints (excluding time to modified renal response), subjects will be imputed as non-responders from time at which the criteria are met, in the following cases:

a) Medication criteria

Subjects who meet any of the following medication criteria:

- Subjects who receive any restricted medication (see [Appendix A](#) and [Appendix B](#)) after randomisation or beyond any protocol allowed thresholds will be considered a non-responder from the time the respective medication was administered up to and including Week 104.
- Subjects who meet any of the corticosteroid criteria (see [Appendix B](#)) will be considered a non-responder from the time the condition is met, up to and including Week 24, Week 52, Week 80 or Week 104, depending on the condition and when it is met.
- Subjects who meet any of the MMF criteria (see [Appendix B](#)) will be considered a non-responder from the time the condition is met, up to and including to Week 24, Week 52, Week 80 or Week 104, depending on the condition and when it is met.

b) Discontinued IP

Subjects who prematurely discontinue from IP, including subjects who withdraw from the study. All subjects who have an infusion of IP within the Week 48 analysis visit window will be determined to have completed treatment in the double-blind treatment period.

Non-responder imputation will be applied at all scheduled visits, including missing visits. If a subject does not have a response at a visit, they will be imputed as a non-responder (note that unless IP was discontinued or any of the medication criteria above are met, LOCF will be applied to missing values at the first missed visit in case of consecutive missed visits and the non-responder imputation will be applied to the response values determined after LOCF imputation. See Section 4.1.4.2 for more details on LOCF).

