4.3 Subgroup analysis

To explore the uniformity of the detected overall treatment effect, subgroup analyses will be performed for the following factors:

- Type I IFN 4-gene test at screening (IFN test-high, IFN test-low)
- 24-hour UPCr at screening ≤ 3 mg/mg, >3 mg/mg
- Age (≥ 18 to 64, ≥ 65 years)
- Placebo response region (low placebo response rate versus high placebo response rate)
Countries with a low placebo response rate versus high placebo response rate are defined as [Low: Australia, Belgium, France, Germany, Italy, South Africa, Spain, United Kingdom, United States], [High: Argentina, Hungary, Republic of Korea, Mexico, Peru, Poland, Russian Federation, Serbia, Taiwan]
- Race (white; black or African American; Asian, native Hawaiian or other Pacific Islander; American Indian or Alaska native; other)
- Screening biopsy classification (class III, class IV, mixed [class III or IV + class V])
- Number of methylprednisolone pulses (1, >1). Pulses are counted during the whole study.
- ADA result (Positive at any time, Negative)
- OCS at baseline (<20 mg/day, ≥ 20 mg/day)
- eGFR at baseline (<60 mL/min/1.73m², ≥ 60 mL/min/1.73m²)

Table 3, Table 4 and Table 5 give an overview of subgroup analyses to be performed at Week 24, 52 and Week 104, respectively. Where necessary (e.g. for subgroup analysis based on stratification factors), the model factors will be reduced. If not stated otherwise, the subgroup analysis will not be performed for a sub-population if any treatment group consists of less than 10 subjects within that sub-population. Where a sub-population contains less than 10 subjects in any treatment group, only ns and treatment estimates will be presented (no treatment comparisons will be presented).

Forest plots will be used to summarise the estimates of the treatment effect for the applicable subgroups.

Table 3 Overview of subgroup analyses at Week 24

Analysis	IFN test	24-hour UPCR	OCS at baseline
24-hour UPCR	X	X	X
CRR	X	X	X

Table 4 Overview of subgroup analyses at Week 52

Analysis	IFN test	24-hour UPCR	Age	Placebo response	Race	Number of methylprednisolone pulses	Screening biopsy	ADA result	OCS at baseline	eGFR at baseline
24-hour UPCR	X	X	X	X	X	X	X	X	X	X
CRR	X	X	X	X	X	X	X		X	X
aCRR	X	X							X	
PRR	X	X				X	X			
Graded CRR	X	X				X	X			
OCS tapering	X	X		X		X	X			

Table 5 Overview of subgroup analyses at Week 104

Analysis	IFN test	24-hour UPCR	OCS at baseline	eGFR at baseline
24-hour UPCR	X	X	X	X
CRR	X	X	X	X

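### The methylprednisolone-pulse subgroup counts pulses over the whole study, so its strata rest largely on post-randomisation events and cannot show whether the treatment effect is uniform

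*SAP*

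**What the plan says.** SAP 4.3 gives the purpose of the subgroup analyses as exploring whether the overall treatment effect is uniform. One listed factor is "Number of methylprednisolone pulses (1, >1). Pulses are counted during the whole study". Table 4 applies it at Week 52 to 24-hour UPCR, CRR, PRR, graded CRR and OCS tapering, and the results go into forest plots. Protocol 8.5.10 lists the same two categories with no counting window, so the whole-study count is the SAP's own addition. SAP section 6 does not mention it.

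The pulses themselves are described as follows.

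- **Day 1.** SAP 1.2.1 schedules a pulse on the day of randomisation, "prior to receiving the IP, unless they have received a methylprednisolone pulse of" at least 500 mg in the preceding 10 days.
- **Up to Week 8.** The same section allows one optional further pulse "for renal or extra-renal disease activity after the Week 0 (Day 1) visit up to and including the Week 8 visit".
- **Pulses that stop IP.** SAP 1.2.5 includes "Receipt of any methylprednisolone pulse after Week 8" among the reasons for stopping IP, as well as more than one pulse after the day of randomisation.
- **After IP has stopped.** SAP 1.2.5 says "Subjects may receive rescue treatment as clinically indicated", and Protocol 3.9.1 says "Subjects who had their IP discontinued will be followed according to the study schedule". A rescue pulse in such a subject would therefore be recorded and counted.

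SAP 1.2 says that the primary analysis also takes in data collected after Week 52.

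**The concern.** A subgroup comparison estimates the treatment effect within a stratum only if treatment cannot influence who is in that stratum. Here the scheduled pulse normally puts a subject in the 1-pulse group. The usual route into the >1 group is a later event, driven by the disease activity that anifrolumab is meant to reduce. If anifrolumab reduces early activity, fewer treated subjects receive a second pulse. The 1-pulse stratum on active treatment then keeps some sicker subjects whose placebo counterparts have moved to >1, and the two arms are no longer alike within either stratum.

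Two features add to this. Some >1 subjects are tied to the outcome by rule: a disallowed pulse stops IP, which removes later UPCR data (SAP 4.2.1) and makes the subject a non-responder (SAP 4.1.4.3). And the count has no Week 52 limit, so a second-year pulse can reassign a subject for a Week 52 result.

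At stake is one row pair in the subgroup tables and forest plots, which a reader could take as information on uniformity when it is not.

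**Working it through.** **Plan's own figures first.** SAP 1.3 gives a ratio of 0.65, an SD of 0.8 on the log scale, 50 subjects per arm (100 pooled against 50) and a two-sided alpha of 0.0499.

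- SE = 0.8 × √(1/50 + 1/100) = 0.1386.
- 95% CI = exp(ln 0.65 ± 1.96 × 0.1386) = 0.50 to 0.85, as stated.
- Minimal detectable ratio = 0.76, as stated.
- Power = 0.8745, against approximately 87% stated.

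**Model (assumptions, not document figures).** Let E be an early activity signal, N(0,1) on placebo and shifted by s = k × ln(0.65)/0.8 on active. The fraction k of the effect present early is 0, 0.5 or 1. A subject has a post-Day 1 pulse if E exceeds a cut c, chosen so that 10% or 25% of placebo do. Week 52 log-UPCR has SD 0.8 and correlation ρ = 0.2, 0.4 or 0.8 with E. The true treatment ratio is 0.65 for everyone.

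In the 1-pulse stratum the mean standardised residual of E is m_P = −φ(c)/Φ(c) on placebo and m_A = −φ(c−s)/Φ(c−s) on active. The apparent log ratio is therefore ln 0.65 + 0.8ρ(m_A − m_P).

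**Worked extreme.** Take a 25% placebo share, k = 1 and ρ = 0.8.

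- c = 0.6745 and s = −0.5385; the active share with a post-Day 1 pulse is 11.3%.
- m_P = −0.4237 and m_A = −0.2154.
- Shift = 0.8 × 0.8 × 0.2083 = 0.133, so the ratio reads 0.65 × exp(0.133) = 0.74.
- SE = 0.8 × √(1/37.5 + 1/88.7) = 0.156, so the shift is 0.86 SE.

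**All cases.** Ratio in the 1-pulse stratum, with the shift in SE in brackets:

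| Placebo share | k | Active share | ρ = 0.2 | ρ = 0.4 | ρ = 0.8 | >1 comparison suppressed |
|---|---|---|---|---|---|---|
| 10% | 0 | 10% | 0.65 (0) | 0.65 (0) | 0.65 (0) | about 100% |
| 10% | 0.5 | 6% | 0.66 (0.07) | 0.66 (0.15) | 0.68 (0.30) | about 100% |
| 10% | 1 | 3% | 0.66 (0.13) | 0.67 (0.26) | 0.70 (0.51) | about 100% |
| 25% | 0 | 25% | 0.65 (0) | 0.65 (0) | 0.65 (0) | 42% |
| 25% | 0.5 | 17% | 0.66 (0.12) | 0.67 (0.23) | 0.70 (0.47) | 89% |
| 25% | 1 | 11% | 0.67 (0.21) | 0.69 (0.43) | 0.74 (0.86) | about 100% |

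The last column is the probability that at least one of three arms of 50 has fewer than 10 subjects in the >1 stratum, from binomial counts. In that case SAP 4.3 shows counts and estimates but no treatment comparison. The column assumes that nobody is in >1 before the first dose. For example, at 25% in every arm, P(fewer than 10 of 50) = 0.164 and 1 − (1 − 0.164)³ = 0.42.

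**Cross-check.** A separate simulation used placebo shares of 15% and 30%, correlations of 0.3 to 0.7 and an early reduction of 0, 0.25 or 0.5 SD. Both strata returned 0.65 when treatment did not change pulse use. Otherwise the 1-pulse stratum read 0.66-0.73 and the >1 stratum 0.68-0.81.

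**Limits.** The model is unadjusted, whereas the planned MMRM adjusts for baseline UPCR and stratification factors. No CRR figure is given, because the model has no imputed non-response.

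**The case against.** The strongest reply is that the SAP claims little for this display. It speaks of exploring, specifies no interaction test, and says in 4.1.3 that nominal p-values outside the testing strategy cannot be read as statistical significance. The factor also stands in the protocol, and the under-10 rule will often hide the >1 comparison. All of that is fair and sets the weight of the point. It does not remove it: the 1-pulse comparison would usually still be shown, with uniformity as its stated purpose.

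The size is also conditional. If treatment does not change pulse use, the shift is exactly zero. The upper end needs the full Week 52 effect to be present early, although the optional pulse is allowed only to Week 8, together with a correlation of 0.8. At a correlation of 0.4 or less the shift is at most 0.43 SE.

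A reader might infer more than the documents support in four places:

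- **Subjects with no category.** A recent pre-randomisation pulse replaces the Day 1 pulse, which suggests a count of zero. But SAP 1.2 includes screening in study duration, so such a pulse would usually be counted. The SAP should say so, but a gap is not established.
- **A >1 group that is purely post-randomisation.** If screening counts, an earlier screening pulse plus the Day 1 pulse gives >1 before any IP. The accurate word is largely, and the suppression figures rest on there being no such subjects.
- **Larger bias from rescue pulses.** UPCR after IP discontinuation is already excluded from the main analysis (SAP 4.2.1), with an exception for those last dosed in the Week 48 window. A bigger shift cannot be put down to the subgroup definition alone.
- **A quantified CRR distortion.** SAP 4.1.4.3 makes a subject who takes restricted medication "after randomisation or beyond any protocol allowed thresholds will be considered a non-responder from the time the respective medication was administered", but the details sit in Appendices A and B, whose text was not available for this check.

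**Conclusion.** The point stands as a minor, exploratory one. As written, the strata are largely defined by events after randomisation that treatment can affect, and no section seen limits the count to baseline. Differences between them are therefore not evidence for or against uniformity of the treatment effect.

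Under the assumptions above, the 1-pulse ratio lies between 0.65 (no distortion) and 0.74, and the >1 comparison is suppressed with probability from about 42% to about 100%. The pulse shares, correlations and early-effect fractions are assumed. Only the ratio, SD and sample size come from the SAP.

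It would be wrong to infer that the primary UPCR test or the CRR test is compromised: neither uses this factor. ADA result, defined as positive at any time in the same list and applied to Week 52 UPCR in Table 4, has the same weakness.

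**What to change.** Take the pulse factor out of the treatment-effect subgroups and forest plots in SAP 4.3 and Table 4. Report post-Day 1 pulses by arm as a descriptive outcome in three periods: up to Week 8, Week 8 to 52, and after Week 52. This table also shows whether pulse use differs by arm, on which the whole distortion depends. Record the departure from Protocol 8.5.10 in SAP section 6, which already records another subgroup change.

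If a pulse subgroup is kept, count only pulses before the first IP dose, and state whether screening pulses count so that every subject has a category. The >1 group may then be too small to show. With three arms of 50 and assumed pre-dose shares of 10%, 20% and 30%, the under-10 rule suppresses the comparison with probability about 100%, 83% and 12%.

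Apply the same reasoning to ADA positivity at any time, at least by labelling that display as descriptive.

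The cost is wording in SAP 4.3, Table 4 and section 6, and at most one re-derived variable, with no new data. Protocol 8.5.10 makes the subgroup analyses optional, so the departure is small. One exploratory display is lost or, under the pre-dose definition, answers a different question.

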5 INTERIM ANALYSES

One interim analysis either for efficacy or futility may be conducted after approximately 80% of subjects have completed the Week 52 visit or would have completed Week 52 if they had not discontinued the study. Primary efficacy and safety analyses will be performed once all data from the main study (up to and including Week 52) is available, cleaned and soft-locked. The study will also be unblinded at this stage for the team performing the analysis.

5.1 Potential Interim analysis for futility

The objective of a potential interim analysis for futility is to give consideration for stopping the study early, should the chance of detecting a statistically significant difference with placebo for the primary endpoint at the final analysis be sufficiently small given the interim data. Non-binding futility rule for stopping the study will be used if a futility analysis is performed. Even though non-binding futility boundary will be used for stopping the study, if interim analysis for futility is performed, a portion of the 2-sided alpha will still be spent. A Peto-Haybittle spending function would be used with a fixed 2-sided p-value threshold of 0.1% at the interim. The p-value threshold at the final analysis will be adjusted to account for the interim analysis, based on the actual observed information fraction for the primary endpoint. Under the assumption that there are 120 subjects included at the interim and 150 subjects at the final analysis, the critical threshold at the final analysis will be 4.99% (East Version 6.4).

Considerations for stopping the study may be given if based on the observed effect at the interim analysis, the probability of detecting a statistically significant difference with placebo for the primary endpoint at the final analysis as measured by the predictive power (Herson, 1979), is no higher than 20%. The predictive power will be derived from the following expression:

$$Predictive\ Power = \Phi \left((1 - \Pi)^{-\frac{1}{2}} \left(z_{0.025} \cdot \sqrt{\Pi} - \hat{\theta}_{fut} \sqrt{I_{fut}} \right) \right),$$

where

- Φ denotes the cumulative distribution function of a standard normal distribution;
- $z_{0.025}$ is the Z-score at the lower tail corresponding to a 2-sided alpha level 0.0499 assuming 120 patients in the interim analysis (lower tail is used instead of upper due to using a logarithmic scale);
- $\hat{\theta}_{fut}$ is the observed at the interim analysis log-transformed relative difference in the change from baseline to Week 52 in 24-hour UPCR between the pooled anifrolumab treatment group versus placebo;
- I_{fut} is the information at the futility analysis $I_{fut} = \{Var(\hat{\theta}_{fut})\}^{-1}$, which can be estimated as $1/SE_{MMRM}^2$, where SE_{MMRM}^2 is the standard error of the relative difference in change from baseline in 24-hour UPCR on a logarithmic scale from the MMRM model for the primary endpoint at the interim analysis;
- Π is the fraction of information $\Pi = \frac{I_{fut}}{I_{fin}} = \frac{\text{number of patients in the interim analysis}}{\text{expected number of patients in the final analysis}}$, if $I_{fin} = \{Var(\hat{\theta}_{fin})\}^{-1}$ is the information at the final analysis.

The above derivation is based on the weighted average of the conditional power over values of the difference with placebo θ , drawn from the posterior distribution below, which is obtained using an uninformative prior (Jennison & Turnbull, 2000):

$$\theta | Z_{fut} \sim N\left(\hat{\theta}_{fut}, \frac{1}{I_{fut}}\right),$$

The conditional power is the conditional probability that the final test statistic will exceed a critical value given the data observed thus far and an assumption about the pattern of the data to be observed in the remainder of the study, expressed as:

$$\text{Conditional Power} = 1 - \Phi\left((1 - \Pi)^{-\frac{1}{2}}\left(\hat{\theta}_{fut}\sqrt{I_{fut}} \cdot \sqrt{\Pi} - z_{0.0245}\right) + \theta \sqrt{\frac{I_{fut}}{\Pi}} \sqrt{1 - \Pi}\right).$$

Based on the above, the corresponding treatment effect boundary providing 20% predictive power can be calculated as:

$$\delta_{fut} = \exp\left\{\left(z_{0.025} + z_{1-20\%}\sqrt{\frac{1}{\Pi} - 1}\right) \sqrt{\frac{\Pi}{I_{fut}}}\right\}$$

An observed effect $\hat{\theta}_{fut}$ worse than δ_{fut} corresponds to a predictive power less than 20%.

